11.2.3. Exploratory Analyses

Exploratory endpoints of this study include correlative work performed on research serum and tissue samples. These are detailed in Section 8.2

11.2.4 Interim analyses

No interim analysis is planned for this study.

11.3 Determination of sample size

There are multiple ongoing studies in various tumor types exploring the activity of durvalumab and tremelimumab. In a published report of the combination in patients with advanced NSCLC treated on a phase Ib study, Grade 3-4 toxicity was observed in 17% of patients. Similarly, in single institution reports of SBRT with the monoclonal antibody, grade 3 or higher toxicity was reported in 6-16% of patients. With 20 patients, toxicity rates can be estimated to within 22% with 95% confidence. Any toxicity with at least 10% prevalence has at least an 87% chance of being observed. With these properties, this design, allows us to reasonably exclude a clinically significant increase in toxicity with the addition of radiation therapy to the durvalumab and tremelimumab combination as defined by the upper bound of the confidence interval.

The response rates to dual CTLA and PDL1 blockade and radiation therapy after prior immunotherapy are unknown. If objective responses are demonstrated, or encouraging progression free survival is observed in the 20 patients enrolled on the study, it would merit further investigation in a larger study powered to examine efficacy endpoints

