Both durvalumab and tremelimumab have well established toxicity profiles as a single agent and in combination. However, the combination of durvalumab tremelimumab and palliative radiation has not been previously studied, this study will include a formal safety analysis in the first 6 patients accrued. Enrollment will be halted until these first 6 patients complete the first two cycles of treatment (8 weeks), and are evaluable for acute toxicities (toxicities reported within the 1st 8 weeks after treatment initiation). Specifically, if 2 or more DLTs (Refer to Section 6.4) are observed, then, durvalumab dosing will be modified to 1500 mg IV Q6 weeks x 9 doses and tremelimumab 75mg IV Q6 weeks x 3 doses for the remaining 14 patients (fixed dosing for patients > 30kg). If 1 or fewer DLTs are observed, then an additional 14 patients will be enrolled and treated at the initial dose and schedule of durvalumab and tremelimumab. Patients in the run in phase who experience DLTs will undergo dose modifications described in Appendix 1.

Toxicities will be graded based on CTCAE v. 4 and summarized as the number and percentage of patients with each type of toxicity. Responses will be summarized as frequencies and percentages. The Kaplan Meier method will be used to estimate overall survival and progression free survival. Outcomes will be calculated from the date of study entry to the date of the corresponding event.

We will use multivariate statistics to test the hypotheses that pretreatment intratumoral immune cell phenotype and PD-L1 expression predict response to therapy, and that therapy alters systemic immunophenotype.

Sample Size Determination:

There are multiple ongoing studies in various tumor types exploring the activity of durvalumab and tremelimumab. In a published report of the combination in patients with advanced NSCLC treated on a phase Ib study, Grade 3-4 toxicity was observed in 17% of patients. Similarly, in single institution reports of SBRT with the monoclonal antibody, grade 3 or higher toxicity was reported in 6-16% of patients. With a 20 patient accrual goal, toxicity rates can be estimated to within 22% with 95% confidence. Any toxicity with at least 10% prevalence has at least an 87% chance of being observed. This design allows us to reasonably exclude a clinically significant increase in toxicity with the addition of radiation therapy to the durvalumab and tremelimumab combination as defined by the upper bound of the confidence interval.

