11.2 Methods of statistical analyses

11.2.1 Safety Analyses

Safety and tolerability is the primary endpoint of this study, and all patients enrolled (including those replaced in the run in phase) will be assessed for this endpoint. Adverse events will be recorded and graded based on CTCAE v. 4, and their relationship to the experimental agents reported.

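### The claim in Section 11.3 and the synopsis that 20 patients can exclude a clinically significant toxicity increase has no stated margin and is unsupported for increases up to about a doubling of the 17% reference

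*Combined protocol and SAP*

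**What the plan says.** Section 11.3 starts from a published report of durvalumab plus tremelimumab in lung cancer, in which "Grade 3-4 toxicity was observed in 17% of patients". It adds a range of 6-16% for Grade 3 or higher toxicity in reports of SBRT with the monoclonal antibody. Two precision figures follow: "With 20 patients, toxicity rates can be estimated to within 22% with 95% confidence" and "Any toxicity with at least 10% prevalence has at least an 87% chance of being observed". From these properties it concludes that the design "allows us to reasonably exclude a clinically significant increase in toxicity with the addition of radiation therapy to the durvalumab and tremelimumab combination". The yardstick for that exclusion is given in the same sentence: "as defined by the upper bound of the confidence interval". In the synopsis, Sample Size Determination draws the same conclusion: "This design allows us to reasonably exclude a clinically significant increase in toxicity".

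The planned analysis is plainer. In the synopsis, under Statistical Methods and Data Analysis, toxicities are "summarized as the number and percentage of patients with each type of toxicity". Section 11.2.1 makes safety and tolerability the primary endpoint and says: "Adverse events will be recorded and graded based on CTCAE v. 4, and their relationship to the experimental agents reported". Neither place lists a confidence interval.

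**The concern.** Excluding an increase by an upper confidence bound needs a rate for the bound to fall below, an event to count, and an interval method. The plan gives the 95% level but no margin, no method and no sidedness. The event is only implied by the Grade 3-4 and Grade 3 or higher reference rates, which differ from each other.

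The two figures offered as support do not fill the gap. A half-width of 22 points exceeds the 17% reference itself. The 87% is the chance of seeing at least one event, which says nothing about bounding a rate from above.

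At stake is the conclusion on the primary endpoint. A final report could cite this sentence as prespecified support for saying that radiation added no important toxicity, while its own interval still contained about twice the reference rate.

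**Working it through.** **Inputs.** n = 20, 95% confidence and the 17% reference come from Section 11.3. Taking 17% as the true rate here is an assumption, since it comes from lung cancer patients. The 75% and 80% benchmarks and the 34% and 39% margins below are chosen for this check; the plan states none of them.

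**The plan's own figures.**
- Worst-case two-sided Wald half-width: 1.96 × √(0.5 × 0.5 / 20) = 21.9 points, which matches 22%. The exact (Clopper-Pearson) interval at 10/20 gives 22.8, so Wald is the plan's apparent method.
- Chance of at least one event at 10% prevalence: 1 − 0.9^20 = 87.8%, which matches 87%.

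**Upper limits and their probabilities.** With x events, the Wald upper limit is x/20 + z × √[(x/20)(1 − x/20)/20], where z = 1.96 (two-sided) or 1.645 (one-sided). The exact limit is the 97.5% (two-sided) or 95% (one-sided) quantile of Beta(x + 1, 20 − x). The second column is the Binomial(20, 0.17) cumulative probability.

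| Events x | P(X ≤ x) at 17% | Wald, two-sided | Wald, one-sided | Exact, two-sided | Exact, one-sided |
|---|---|---|---|---|---|
| 2 | 31.5% | 23.1% | 21.0% | 31.7% | 28.3% |
| 3 | 55.0% | 30.6% | 28.1% | 37.9% | 34.4% |
| 4 | 75.6% | 37.5% | 34.7% | 43.7% | 40.1% |
| 5 | 89.0% | 44.0% | 40.9% | 49.1% | 45.6% |

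**Expected result.** At 17%, 20 × 0.17 = 3.4 events are expected. With 3 or 4 events the two-sided limits run from 30.6% (Wald, 3 events) to 43.7% (exact, 4 events): 30.6/17 = 1.8 and 43.7/17 = 2.6 times the reference.

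**Lowest rate excluded, by benchmark.**
- At least 75% probability: the limit must still exclude at 4 events (75.6%). That gives 37.5% with two-sided Wald, and 34.7% to 43.7% across methods.
- At least 80% probability: 4 events falls short, so the limit must exclude at 5 events (89.0%). That gives 44.0% with two-sided Wald, and 40.9% to 49.1% across methods.

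Wilson, Agresti-Coull and Jeffreys limits fall between these ends.

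**A doubling, 2 × 17% = 34%.** Two-sided exact limits fall below 34% only with 2 events or fewer, probability 31%. Wald limits, one- or two-sided, do so with 3 or fewer, probability 55%. These are the chances when radiation adds no toxicity at all.

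**The case against.** The strongest reply is that a claim without a number is undefined rather than false. The plan speaks of a clinically significant increase, not a moderate one, and a large enough margin would be excluded. Section 1.4.2.3 cites treatment-related Grade 3 or 4 events in 53% of melanoma patients on a same-class combination. If a rate that high were the concern (an assumption, not the plan's), even two-sided exact limits would exclude it with 5 events or fewer, an 89.0% chance at a true 17%. On the plan's apparent Wald method, a margin of 17% + 22% = 39% would be excluded with 76% probability, which some would call reasonable. The 80% benchmark is also external, and 4 events misses it by only 4.4 points.

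Much of this stands. A reader might infer that the claim is false whatever the margin, or that 41% to 49% is the threshold the design implies. The documents support neither: the answer depends on a margin they leave open, and the range moves with the benchmark and method. Nor is the event wholly missing, because the reference grades point towards it.

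What does not stand is the inference itself. The plan derives exclusion from the 22% and 87% figures, and it does not follow from them. Under every interval checked, the chance of excluding a doubling is little better than even at best. That no decision rule uses the sentence limits the consequence, but the sentence still concerns the primary endpoint.

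**Conclusion.** The point holds. The exclusion claim is unsupported for increases up to about a doubling of the 17% reference, and could hold only for a much larger margin that the plan does not state. This is more than missing detail, because the plan presents the property as following from figures that do not yield it.

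The sizes assume a true rate of 17% and all 20 patients pooled. The conclusion about a doubling does not depend on the 75% or 80% benchmark.

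Two further inferences should be avoided. The sample-size arithmetic is not in error, since both stated figures reproduce. Nor is patient protection weakened: the run-in DLT rule (Sections 6.2 and 6.4) and the Grade 4 stopping rule (Section 3.3) do not rely on this sentence. What is affected is the safety conclusion at the end of the trial. The change is one the plan should make, without bearing on trial conduct.

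**What to change.** In Section 11.3 and the synopsis, replace the exclusion sentence with a precision statement, for example: *With 20 patients the two-sided exact 95% upper limit is 31.7%, 37.9%, 43.7% and 49.1% for 2, 3, 4 and 5 events; the study estimates the toxicity rate and is not sized to exclude a moderate increase over the 17% reference.*

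If the sponsor prefers to keep an exclusion claim, it should state its own margin, the event, the interval method with sidedness, and the resulting probability of exclusion.

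In Section 11.2.1, add the proportion of patients with at least one Grade 3 or higher adverse event, regardless of attribution to drug or radiation, with a 95% confidence interval by the method named in 11.3. Counting events regardless of attribution matters because the claim is about adding radiation, and a drug-related count would miss events attributed to radiation alone.

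The cost is a less favourable stated property and one extra interval. No additional patients or data are needed.

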12. ETHICAL AND REGULATORY REQUIREMENTS

12.1 Ethical conduct of the study

The study will be performed in accordance with ethical principles that have their origin in the Declaration of Helsinki and are consistent with ICH/Good Clinical Practice, and applicable regulatory requirements Subject data protection.

12.2 Ethics and regulatory review

The protocols will be approved and reviewed by the Cancer Consortium Scientific Review Committee (SRC) and the Institutional Review Board (IRB). The protocol once activated will be reviewed at least annually by both institutional entities.

12.3 Informed consent

Consent must be documented by the subject's dated signature or by the subject's legally acceptable representative's dated signature on a consent form along with the dated signature of the person conducting the consent discussion.

A copy of the signed and dated consent form should be given to the subject before participation in the trial.

The initial informed consent form, any subsequent revised written informed consent form and any written information provided to the subject must receive the IRB/ERC's approval/favorable

opinion in advance of use. The subject or his/her legally acceptable representative should be informed in a timely manner if new information becomes available that may be relevant to the subject's willingness to continue participation in the trial. The communication of this information will be provided and documented via a revised consent form or addendum to the original consent form that captures the subject's dated signature or by the subject's legally acceptable representative's dated signature.

The informed consent will adhere to IRB/ERC requirements, applicable laws and regulations and Sponsor requirements.

12.4 Changes to the protocol and informed consent form

The protocol, the proposed informed consent and all forms of participant information related to the study (e.g. advertisements used to recruit participants) will be reviewed and approved by the Cancer Consortium IRB and Scientific Review Committee (SRC). Any changes made to the protocol will be submitted as a modification and will be approved by the IRB prior to implementation.

12. 5Audits and inspections

The study will be audited and inspected by the Cancer Center Consortium.

13. STUDY MANAGEMENT

13.1 Training of study site personnel

All investigators on the protocol will receive formal training in the ethical conduct of human research. Institutional support of trial auditing is provided in accordance with the Cancer Consortium's data and safety monitoring plan

13.2 Monitoring of the study

13.2.1 Source data

The Fred Hutchinson/University of Washington Consortium Data and Safety Monitoring Committee (DSMC) will be the monitoring entity for this study in accordance with the Cancer Consortium's Data Safety Monitoring Plan.

13.3 Study timetable and end of study

The end of the study is defined as the last visit of the last patient undergoing the study. Either AstraZeneca or the Investigator may terminate the entire study prematurely if concerns for safety arise within this study or other durvalumab studies.

14. DATA MANAGEMENT

The Protocol Director, or her designees, will prepare and maintain adequate and accurate participant case histories with observations and other data pertinent to the study. Original source documents should be transcribed to Case Report Forms (CRFs) and used to analyze the study data. Source documents include hospital records, clinical charts, laboratory and pharmacy records, and recorded electronic data.

All data required by the trial will be entered onto paper and electronic case report forms. Any corrections to data required into the paper case report forms must be made in such a way that the original entry is not obscured. Only designated study staff will enter data for study participants after study visits. Case report forms will be checked against source document data by study staff.

Patient records will be kept in a secure location at the University of Washington accessible only to research authorized personnel. The patient identity will be kept as confidential as possible as required by law. Except as required by law, the patient will not be identified by name, social security number, address, telephone number, or any other direct personal identifier. Study subjects will be assigned an ID code. Information about the code will be kept in a secure location and access limited to research study personnel. The results of this research study may be presented at scientific or medical meetings or published in scientific journals. However, the patient identity will not be disclosed. The patient's personal data which may be included in the investigator's database shall be treated in compliance with all applicable laws and regulations.

Trial oversight will be carried out by the protocol director, [name], and her research staff. They will meet weekly to review recently acquired data and adverse events. The data recorded within the research charts and protocol database is compared with the actual data that is available from the medical record and/or clinical histories. Data detailed in the research case report forms includes the nature and severity of all toxicities, which are also reported as described above.

14.1 Study governance and oversight

The safety of all AstraZeneca clinical studies is closely monitored on an ongoing basis by AstraZeneca representatives in consultation with Patient Safety. Issues identified will be addressed; for instance, this could involve amendments to the study protocol and letters to Investigators.

15. INVESTIGATIONAL PRODUCT AND OTHER TREATMENTS

15.1 Identity of investigational product(s)

Table 8. List of investigational products for this study

Investigational product	Dosage form and strength	Manufacturer
Durvalumab (MEDI4736)	50 mg/mL solution for infusion after dilution	AstraZeneca/MedImmune
Tremelimumab	20mg/mL solution for infusion after dilution	AstraZeneca/MedImmune

Dosing Modification and Toxicity Management Guidelines for Immune-mediated, Infusion Related, and Non Immune-mediated Reactions (MEDI4736 Monotherapy or Combination therapy with Tremelimumab or Tremelimumab Monotherapy) 19 August 2016 Version

Dose Modifications	Toxicity Management
Drug administration modifications of study drug/study regimen will be made to manage potential immune-related AEs based on severity of treatment-emergent toxicities graded per NCI CTCAE v4.03. In addition to the criteria for permanent discontinuation of study drug/study regimen based on CTC grade/severity (table below), permanently discontinue study drug/study regimen for the following conditions: 
 Inability to reduce corticosteroid to a dose of ≤ 10 mg of prednisone per day (or equivalent) within 12 weeks after last dose of study drug/study regimen Recurrence of a previously experienced Grade 3 treatment-related AE following resumption of dosing 	It is recommended that management of irAEs follows the guidelines presented in this table: 
 Patients should be thoroughly evaluated to rule out any alternative etiology (eg, disease progression, concomitant medications, and infections). In the absence of a clear alternative etiology, all events should be considered potentially immune related. Symptomatic and topical therapy should be considered for low-grade (Grade 1 or 2, unless otherwise specified) events. For persistent (>3 to 5 days) low-grade (Grade 2) or severe (Grade ≥ 3) events, promptly start prednisone 1 to 2 mg/kg/day PO or IV equivalent. If symptoms recur or worsen during corticosteroid tapering (28 days of taper), increase the corticosteroid dose (prednisone dose [eg, up to 2 to 4 mg/kg/day PO or IV equivalent]) until stabilization or improvement of symptoms, then resume corticosteroid tapering at a slower rate (>28 days of taper). More potent immunosuppressives such as TNF inhibitors (eg, infliximab) (also refer to the individual sections of the irAE for specific type of immunosuppressive) should be considered for events not responding to systemic steroids. Discontinuation of study drug/study regimen is not mandated for Grade 3/Grade 4 inflammatory reactions attributed to local tumor response (eg, inflammatory reaction at sites of metastatic disease and lymph nodes). Continuation of study drug/study regimen in this situation should be based upon a benefit/risk analysis for that patient.
Grade 1 No dose modification	
Grade 2 Hold study drug/study regimen dose until Grade 2 resolution to Grade ≤ 1 . If toxicity worsens, then treat as Grade 3 or Grade 4. Study drug/study regimen can be resumed once event stabilizes to Grade ≤ 1 after completion of steroid taper. Patients with endocrinopathies who may require prolonged or continued steroid replacement can be retreated with study drug/study regimen on the following conditions: 
 The event stabilizes and is controlled. The patient is clinically stable as per Investigator or treating physician's clinical judgement. Doses of prednisone are at ≤ 10 mg/day or equivalent. 	
Grade 3 Depending on the individual toxicity, study drug/study regimen may be permanently discontinued. Please refer to guidelines below.	
Grade 4 Permanently discontinue study drug/study regimen.	
Note: For Grade ≥ 3 asymptomatic amylase or lipase levels, hold study drug/study regimen, and if complete work up shows no evidence of pancreatitis, study drug/study regimen may be continued or resumed.	

**Dosing Modification and Toxicity Management Guidelines for Immune-mediated,
Infusion Related, and Non Immune-mediated Reactions (MEDI4736
Monotherapy or Combination therapy with Tremelimumab or
Tremelimumab Monotherapy) 19 August 2016 Version**

Dose Modifications	Toxicity Management

Note: For Grade 3 and above asymptomatic amylase or lipase levels hold study drug/regimen and if complete work up shows no evidence of pancreatitis, may continue or resume study drug/regimen
	

(i) AE Adverse event; CTC Common Toxicity Criteria; CTCAE Common Terminology Criteria for Adverse Events; irAE Immune-related adverse event; IV intravenous; NCI National Cancer Institute; PO By mouth.
	

Specific Immune-mediated Reactions

Adverse Events	Severity Grade of the Event (NCI CTCAE version 4.03)	Dose Modifications	Toxicity Management
Pneumonitis/ILD	Any Grade	General Guidance	
For Any Grade:
 
 Monitor patients for signs and symptoms of pneumonitis or ILD (new onset or worsening shortness of breath or cough). Patients should be evaluated with imaging and pulmonary function tests, including other diagnostic procedures as described below. Initial work-up may include clinical evaluation, monitoring of oxygenation via pulse oximetry (resting and exertion), laboratory work-up, and high-resolution CT scan.
Grade 1 (asymptomatic, clinical or diagnostic observations only; intervention not indicated)	No dose modifications required. However, consider holding study drug/study regimen dose as clinically appropriate and during diagnostic work-up for other etiologies.		
For Grade 1 (radiographic changes only):
 
 Monitor and closely follow up in 2 to 4 days for clinical symptoms, pulse oximetry (resting and exertion), and laboratory work-up and then as clinically indicated. Consider pulmonary and infectious disease consult.
Grade 2 (symptomatic; medical intervention indicated; limiting instrumental ADL)	
Hold study drug/study regimen dose until Grade 2 resolution to Grade ≤ 1.
 
 If toxicity worsens, then treat as Grade 3 or Grade 4. If toxicity improves to Grade ≤ 1, then the decision to reinitiate study drug/study regimen will be based upon treating physician's clinical judgment and after completion of steroid taper. 		
For Grade 2 (mild to moderate new symptoms):
 
 Monitor symptoms daily and consider hospitalization. Promptly start systemic steroids (eg, prednisone 1 to 2 mg/kg/day PO or IV equivalent). Reimage as clinically indicated. If no improvement within 3 to 5 days, additional workup should be considered and prompt treatment with IV methylprednisolone 2 to 4 mg/kg/day started If still no improvement within 3 to 5 days despite IV methylprednisolone at 2 to 4 mg/kg/day, promptly start immunosuppressive therapy such as TNF inhibitors (eg, infliximab at 5 mg/kg every

Specific Immune-mediated Reactions

Adverse Events	Severity Grade of the Event (NCI CTCAE version 4.03)	Dose Modifications	Toxicity Management
		2 weeks). Caution: It is important to rule out sepsis and refer to infliximab label for general guidance before using infliximab.	
 – Once the patient is improving, gradually taper steroids over ≥ 28 days and consider prophylactic antibiotics, antifungals, or anti-PCP treatment (refer to current NCCN guidelines for treatment of cancer-related infections (Category 2B recommendation)^a – Consider pulmonary and infectious disease consult. – Consider, as necessary, discussing with study physician.
Grade 3 or 4 (Grade 3: severe symptoms; limiting self-care ADL; oxygen indicated)	Permanently discontinue study drug/study regimen.	For Grade 3 or 4 (severe or new symptoms, new/worsening hypoxia, life-threatening):	
 – Promptly initiate empiric IV methylprednisolone 1 to 4 mg/kg/day or equivalent. – Obtain pulmonary and infectious disease consult. – Hospitalize the patient. – Supportive care (eg, oxygen). – If no improvement within 3 to 5 days, additional workup should be considered and prompt treatment with additional immunosuppressive therapy such as TNF inhibitors (eg, infliximab at 5 mg/kg every 2 weeks dose) started. Caution: rule out sepsis and refer to infliximab label for general guidance before using infliximab. – Once the patients is improving, gradually taper steroids over ≥ 28 days and consider prophylactic antibiotics, antifungals, and, in particular, anti-PCP treatment (refer to current NCCN guidelines for treatment of

Specific Immune-mediated Reactions

Adverse Events	Severity Grade of the Event (NCI CTCAE version 4.03)	Dose Modifications	Toxicity Management
			cancer-related infections (Category 2B recommendation). ^a
Diarrhea/Enterocolitis	Any Grade	General Guidance	
For Any Grade:
 
 Monitor for symptoms that may be related to diarrhea/enterocolitis (abdominal pain, cramping, or changes in bowel habits such as increased frequency over baseline or blood in stool) or related to bowel perforation (such as sepsis, peritoneal signs, and ileus). Patients should be thoroughly evaluated to rule out any alternative etiology (eg, disease progression, other medications, or infections), including testing for clostridium difficile toxin, etc. Steroids should be considered in the absence of clear alternative etiology, even for low-grade events, in order to prevent potential progression to higher grade event. Use analgesics carefully; they can mask symptoms of perforation and peritonitis.
Grade 1 (stool frequency of <4 over baseline per day)	No dose modifications.		
For Grade 1:
 
 Monitor closely for worsening symptoms. Consider symptomatic treatment, including hydration, electrolyte replacement, dietary changes (eg, American Dietetic Association colitis diet), and loperamide. Use probiotics as per treating physician's clinical judgment.
Grade 2 (stool frequency of 4 to 6 over baseline per day)	Hold study drug/study regimen until resolution to Grade ≤1 • If toxicity worsens, then treat as Grade 3 or Grade 4.		
For Grade 2:
 
 Consider symptomatic treatment, including hydration, electrolyte replacement, dietary changes (eg, American Dietetic Association colitis diet), and loperamide and/or budesonide.

Specific Immune-mediated Reactions

Adverse Events	Severity Grade of the Event (NCI CTCAE version 4.03)	Dose Modifications	Toxicity Management
		
 • If toxicity improves to Grade ≤ 1, then study drug/study regimen can be resumed after completion of steroid taper. 	
 – Promptly start prednisone 1 to 2 mg/kg/day PO or IV equivalent. – If event is not responsive within 3 to 5 days or worsens despite prednisone at 1 to 2 mg/kg/day PO or IV equivalent, GI consult should be obtained for consideration of further workup, such as imaging and/or colonoscopy, to confirm colitis and rule out perforation, and prompt treatment with IV methylprednisolone 2 to 4 mg/kg/day started. – If still no improvement within 3 to 5 days despite 2 to 4 mg/kg IV methylprednisolone, promptly start immunosuppressives such as infliximab at 5 mg/kg once every 2 weeks. Caution: it is important to rule out bowel perforation and refer to infliximab label for general guidance before using infliximab. – Consult study physician if no resolution to Grade ≤ 1 in 3 to 4 days. – Once the patient is improving, gradually taper steroids over ≥ 28 days and consider prophylactic antibiotics, antifungals, and anti-PCP treatment (refer to current NCCN guidelines for treatment of cancer-related infections [Category 2B recommendation]).^a
Grade 3 or 4 (Grade 3: stool frequency of ≥ 7 over baseline per day; Grade 4: life threatening consequences)	Permanently discontinue study drug/study regimen.	For Grade 3 or 4:	
 – Promptly initiate empiric IV methylprednisolone 2 to 4 mg/kg/day or equivalent. – Monitor stool frequency and volume and maintain hydration. – Urgent GI consult and imaging and/or colonoscopy as appropriate. – If still no improvement within 3 to 5 days of IV

Specific Immune-mediated Reactions

Adverse Events	Severity Grade of the Event (NCI CTCAE version 4.03)	Dose Modifications	Toxicity Management
			
methylprednisolone 2 to 4 mg/kg/day or equivalent, promptly start further immunosuppressives (eg infliximab at 5 mg/kg once every 2 weeks). Caution: Ensure GI consult to rule out bowel perforation and refer to infliximab label for general guidance before using infliximab.
 
 – Once the patient is improving, gradually taper steroids over ≥28 days and consider prophylactic antibiotics, antifungals, and anti-PCP treatment (refer to current NCCN guidelines for treatment of cancer-related infections [Category 2B recommendation]).^a
Hepatitis (elevated LFTs) Infliximab should not be used for management of immune-related hepatitis.	Any Grade	General Guidance	
For Any Grade:
 
 – Monitor and evaluate liver function test: AST, ALT, ALP, and TB. – Evaluate for alternative etiologies (eg, viral hepatitis, disease progression, concomitant medications).
	Grade 1 AST or ALT > to 3 × ULN and/or TB > to 1.5 × ULN)	No dose modifications. 
 • If it worsens, then treat as Grade 2 event. 	
For Grade 1:
 
 – Continue LFT monitoring per protocol.
	Grade 2 (AST or ALT > 3 to 5 × ULN and/or TB > 1.5 to 3.0 × ULN)	Hold study drug/study regimen dose until Grade 2 resolution to Grade ≤1. 
 • If toxicity worsens, then treat as Grade 3 or Grade 4. • If toxicity improves to Grade ≤1 or baseline, resume study drug/study regimen after completion of steroid taper. 	
For Grade 2:
 
 – Regular and frequent checking of LFTs (eg, every 1 to 2 days) until elevations of these are improving or resolved. – If no resolution to Grade ≤1 in 1 to 2 days, discuss with study physician. – If event is persistent (>3 to 5 days) or worsens, promptly start prednisone 1 to 2 mg/kg/day PO or IV equivalent. – If still no improvement within 3 to 5 days despite 1 to 2 mg/kg/day of prednisone PO

Specific Immune-mediated Reactions

Adverse Events	Severity Grade of the Event (NCI CTCAE version 4.03)	Dose Modifications	Toxicity Management
			
or IV equivalent, consider additional workup and start prompt treatment with IV methylprednisolone 2 to 4 mg/kg/day.
 
 – If still no improvement within 3 to 5 days despite 2 to 4 mg/kg/day of IV methylprednisolone, promptly start immunosuppressives (mycophenolate mofetil)^a Discuss with study physician if mycophenolate mofetil is not available. Infliximab should NOT be used. – Once the patient is improving, gradually taper steroids over ≥28 days and consider prophylactic antibiotics, antifungals, and anti-PCP treatment (refer to current NCCN guidelines for treatment of cancer-related infections [Category 2B recommendation]).^a
	
Grade 3 or 4
 
(Grade 3: AST or ALT >5 to 20 × ULN and/or TB >3.0 to 10 × ULN)
 
(Grade 4: AST or ALT >20 × ULN and/or TB >10 × ULN)
	
For Grade 3:
 
For elevations in transaminases ≤8 × ULN, or elevations in bilirubin ≤5 × ULN:
 
 • Hold study drug/study regimen dose until resolution to Grade ≤1 or baseline 
• Resume study drug/study regimen if elevations downgrade to Grade ≤1 or baseline within 14 days and after completion of steroid taper.
 
• Permanently discontinue study drug/study regimen if the elevations do not downgrade to Grade ≤1 or baseline within 14 days
	
For Grade 3 or 4:
 
 – Promptly initiate empiric IV methylprednisolone at 1 to 4 mg/kg/day or equivalent. – If still no improvement within 3 to 5 days despite 1 to 4 mg/kg/day methylprednisolone IV or equivalent, promptly start treatment with immunosuppressive therapy (mycophenolate mofetil). Discuss with study physician if mycophenolate is not available. Infliximab should NOT be used. – Perform hepatology consult, abdominal workup, and imaging as appropriate. – Once the patient is improving, gradually taper steroids over ≥28 days and consider prophylactic antibiotics, antifungals, and anti-PCP treatment (refer to current NCCN guidelines for treatment

Specific Immune-mediated Reactions

Adverse Events	Severity Grade of the Event (NCI CTCAE version 4.03)	Dose Modifications	Toxicity Management
		For elevations in transaminases $>8 \times$ ULN or elevations in bilirubin $>5 \times$ ULN, discontinue study drug/study regimen.	of cancer-related infections [Category 2B recommendation]). ^a
		Permanently discontinue study drug/study regimen for any case meeting Hy's law criteria (AST and/or ALT $>3 \times$ ULN + bilirubin $>2 \times$ ULN without initial findings of cholestasis (i.e., elevated alkaline P04) and in the absence of any alternative cause. ^b	
		For Grade 4: Permanently discontinue study drug/study regimen.	
Nephritis or renal dysfunction (elevated serum creatinine)	Any Grade	General Guidance	For Any Grade: 
 Consult with nephrologist. Monitor for signs and symptoms that may be related to changes in renal function (eg, routine urinalysis, elevated serum BUN and creatinine, decreased creatinine clearance, electrolyte imbalance, decrease in urine output, or proteinuria). Patients should be thoroughly evaluated to rule out any alternative etiology (eg, disease progression or infections). Steroids should be considered in the absence of clear alternative etiology even for low-grade events (Grade 2), in order to prevent potential progression to higher grade event.
Grade 1 (Serum creatinine > 1 to $1.5 \times$ baseline; $>$ ULN to $1.5 \times$ ULN)	No dose modifications.	For Grade 1: 
 Monitor serum creatinine weekly and any accompanying symptoms. 
 If creatinine returns to baseline, resume its 	

Specific Immune-mediated Reactions

Adverse Events	Severity Grade of the Event (NCI CTCAE version 4.03)	Dose Modifications	Toxicity Management
			
regular monitoring per study protocol.
 
 • If creatinine worsens, depending on the severity, treat as Grade 2, 3, or 4. – Consider symptomatic treatment, including hydration, electrolyte replacement, and diuretics.
Grade 2 (serum creatinine >1.5 to $3.0 \times$ baseline; >1.5 to $3.0 \times$ ULN)	
Hold study drug/study regimen until resolution to Grade ≤ 1 or baseline.
 
 • If toxicity worsens, then treat as Grade 3 or 4. • If toxicity improves to Grade ≤ 1 or baseline, then resume study drug/study regimen after completion of steroid taper. 		
For Grade 2:
 
 – Consider symptomatic treatment, including hydration, electrolyte replacement, and diuretics. – Carefully monitor serum creatinine every 2 to 3 days and as clinically warranted. – Consult nephrologist and consider renal biopsy if clinically indicated. – If event is persistent (>3 to 5 days) or worsens, promptly start prednisone 1 to 2 mg/kg/day PO or IV equivalent. – If event is not responsive within 3 to 5 days or worsens despite prednisone at 1 to 2 mg/kg/day PO or IV equivalent, additional workup should be considered and prompt treatment with IV methylprednisolone at 2 to 4 mg/kg/day started. – Once the patient is improving, gradually taper steroids over ≥ 28 days and consider prophylactic antibiotics, antifungals, and anti-PCP treatment (refer to current NCCN guidelines for treatment of cancer-related infections [Category 2B recommendation]).^a – When event returns to baseline, resume study drug/study regimen and routine serum creatinine monitoring per study protocol.

Specific Immune-mediated Reactions

Adverse Events	Severity Grade of the Event (NCI CTCAE version 4.03)	Dose Modifications	Toxicity Management
	Grade 3 or 4 (Grade 3: serum creatinine $>3.0 \times$ baseline; >3.0 to $6.0 \times$ ULN; Grade 4: serum creatinine $>6.0 \times$ ULN)	Permanently discontinue study drug/study regimen.	
For Grade 3 or 4:
 
 – Carefully monitor serum creatinine on daily basis. – Consult nephrologist and consider renal biopsy if clinically indicated. – Promptly start prednisone 1 to 2 mg/kg/day PO or IV equivalent. – If event is not responsive within 3 to 5 days or worsens despite prednisone at 1 to 2 mg/kg/day PO or IV equivalent, additional workup should be considered and prompt treatment with IV methylprednisolone 2 to 4 mg/kg/day started. – Once the patient is improving, gradually taper steroids over ≥ 28 days and consider prophylactic antibiotics, antifungals, and anti-PCP treatment (refer to current NCCN guidelines for treatment of cancer-related infections [Category 2B recommendation]).^a
Rash (excluding bullous skin formations)	Any Grade (refer to NCI CTCAE v 4.03 for definition of severity/grade depending on type of skin rash)	General Guidance	
For Any Grade:
 
 – Monitor for signs and symptoms of dermatitis (rash and pruritus). – IF THERE IS ANY BULLOUS FORMATION, THE STUDY PHYSICIAN SHOULD BE CONTACTED AND STUDY DRUG DISCONTINUED.
	Grade 1	No dose modifications.	
For Grade 1:
 
 – Consider symptomatic treatment, including oral antipruritics (eg, diphenhydramine or hydroxyzine) and topical therapy (eg, urea cream).
	Grade 2	For persistent (>1 to 2 weeks) Grade 2 events, hold scheduled study drug/study regimen until resolution to Grade ≤ 1 or baseline.	
For Grade 2:
 
 – Obtain dermatology consult. – Consider symptomatic treatment, including oral antipruritics (eg, diphenhydramine or

Specific Immune-mediated Reactions

Adverse Events	Severity Grade of the Event (NCI CTCAE version 4.03)	Dose Modifications	Toxicity Management
		
 • If toxicity worsens, then treat as Grade 3. • If toxicity improves to Grade ≤ 1 or baseline, then resume drug/study regimen after completion of steroid taper. 	
hydroxyzine) and topical therapy (eg, urea cream).
 
 – Consider moderate-strength topical steroid. – If no improvement of rash/skin lesions occurs within 3 to 5 days or is worsening despite symptomatic treatment and/or use of moderate strength topical steroid, discuss with study physician and promptly start systemic steroids such as prednisone 1 to 2 mg/kg/day PO or IV equivalent. – Consider skin biopsy if the event is persistent for > 1 to 2 weeks or recurs.
